8.4 Inclusion Criteria

Subjects with CSU are eligible to enroll in the study if they meet all of the following criteria.

- 1) Subject is able to understand the information on the study, has the capacity to consent, and has provided written informed consent.
- 2) Male and female subjects ≥ 18 years of age at the time of screening.
- 3) CSU diagnosis for ≥ 6 months.
- 4) Diagnosis of moderate-severe CSU refractory to H1-AH at a minimum of the licensed dose at the licensed frequency at the time of randomization as defined by the following:
 - Presence of hives and itch for ≥ 6 consecutive weeks prior to Screening Visit 1.
 - UAS7 score (range 0–42) ≥16 and HSS7 score (range 0–21) ≥8 during the 7 consecutive days prior to screening Day -7 Phone Visit and during the 7 consecutive days prior to randomization (Day 1).
- 5) Subjects that are omalizumab-naïve or omalizumab-exposed. Omalizumab-exposed subjects are those that have demonstrated secondary loss of response, intolerance, or lack of access to biologics due to economic reasons.
- 6) Subjects must be on a stable dose of H1-AH, between 1× and 4× of the licensed dose and at the licensed dosing frequency, for treatment of CSU for at least 1 week prior to screening and willing to remain on a stable dose throughout the study.
- 7) Able and compliant with completing a daily symptom eDiary for the duration of the study and adherent to the study visit schedules.
- 8) Female subjects must be either postmenopausal (defined as no menses for 12 months without an alternative medical cause) with FSH level >30 mIU/mL at screening or surgically sterile (tubal ligation, hysterectomy, or bilateral oophorectomy) for at least 3 months or, if of childbearing potential, have a negative serum pregnancy test and agree to use a highly effective method of contraception as defined in this protocol or abstain from sexual activity,

if compliant with preferred and usual lifestyle of the subject, from screening until the end of the study or for 120 days following the last dose of study drug, whichever is longer.

In the case of a postmenopausal female subject with FSH level ≤30 mIU/mL at screening, the subject will be required to have a negative serum pregnancy test during the screening period and will also be required to have a negative urine dipstick pregnancy test prior to dosing and at each study visit.

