10.4 Study Drug Dosage and Dosage Regimen

Subjects will be randomly assigned through the IRT system to an active dose group of 6 doses of lirentelimab SC or placebo SC (Table 2).

Study drug will comprise 1 SC injection of 2 mL administered in the front of the thigh with a 27-gauge needle. Injection sites should be alternated between each thigh for subsequent injections. Maximum volume administered per SC injection will be 2 mL as indicated in the study Pharmacy Manual on Day 1 (±3), Dose 1; Day 15 (±5), Dose 2; Day 29 (±5), Dose 3; Day 43 (±5), Dose 4; Day 57 (±5), Dose 5; and Day 71 (±5), Dose 6.

Table 2 Study Drug Administration

Route	Dose (6 Doses Biweekly Over 10 Weeks)	Total Injection Volume
Subcutaneous	300 mg lirentelimab SC or Placebo SC	2 mL

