11.4 Breaking the Blind

Breaking the blind in a clinical study on an emergency basis by the site should only occur when knowledge of the treatment to which a subject was allocated would have implications for the emergency medical management of the subject, if required for regulatory reporting, or if there is a pregnancy during the pregnancy reporting period.

If necessary, emergency breaking of the blind can be conducted through the IRT by the Investigator or other registered site users and/or the Medical Monitor. Whenever possible, the Investigator should contact the Medical Monitor before an emergency unblinding. Reason for

unblinding, person conducting the unblinding, personnel who know the unblinded treatment, and date/time of unblinding will be recorded.

12. Study Procedures and Guidelines

Table 1 provides the schedule of assessments depicting the required testing procedures to be performed for the duration of the study. When multiple evaluations are scheduled at the same time point, the priority for each will be as follows:

- At the clinic:
 - 1) UAS7, forms, and Atopic Conditions Questionnaire.
 - 2) Vital signs will be obtained after the subject has been at rest for ≥ 5 minutes.
 - 3) Physical examinations can be performed, and urine samples can be collected either before or after other evaluations, unless otherwise specified.

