- 7) Perform urine pregnancy test if subject is of childbearing potential.
- 8) Collect vital signs.
- 9) Perform symptom-directed physical exam, as needed.
- 10) Collect blood for CBC, chemistry, and PK.
- 11) Collect blood for total serum IgE.

13.13 Day 155 (±5) or 84 Days Post-Dose – Follow-up Visit 3

- 1) Assess the subject for AE and SAE.
- 2) Document any changes to concomitant medications.
- 3) Assess UPDD and (if applicable) compliance.
- 4) Perform UAS7 and assessments.
- 5) Have subject complete.
- 6) Collect body weight (in kg).
- 7) Collect urine for urinalysis.
- 8) Perform urine pregnancy test if subject is of childbearing potential.

- 9) Collect vital signs.
- 10) Perform symptom-directed physical exam, as needed.
- 11) Collect blood for CBC, chemistry, PK, and ADA.
- 12) Collect blood for total serum IgE.

For Early Termination: Perform the visit 14, 56, or 84 (\pm 5) days after the last dose of study drug or prior to this, if necessary, to ensure compliance with the visit.

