14.8.3 Pregnancy Reporting

Pregnancies are captured if they occur in female subjects or in the sexual partners of male subjects from the time the subject is first exposed to the investigational product through the time of study completion or ET of the double-blind period or the OLE period, whichever is longer.

Female subjects must be instructed to discontinue all study drugs and inform the Investigator immediately if they become pregnant during the study. Male subjects must inform the Investigator immediately if their partner becomes pregnant during the study.

The Investigator must report any pregnancy to Allakos within 24 hours of becoming aware of it using the provided pregnancy reporting forms. Female subjects must be immediately discontinued from study drug. An uncomplicated pregnancy will not be considered an AE or SAE, but all pregnancies in subjects who received lirentelimab will be followed through term. For male subjects with female partners who become pregnant, the site will ask the father (the study subject) to provide information about the outcome of the pregnancy and information about the baby. If detailed health information about the mother is requested by Allakos, a Pregnant Partner Information Release Form will be provided to the site for the mother to sign.

Any congenital abnormalities noted at birth in the offspring of a subject who received lirentelimab will be reported as a SAE. If the subject received lirentelimab, the outcome of any pregnancy and the presence or absence of any congenital abnormality will be recorded in the source documentation and reported to the Medical Monitor and Sponsor via the pregnancy reporting form.

14.8.4 **AESI Reporting**

Beginning from the time of first SC injection of study drug and ending at the time of study completion or ET of the double-blind period or the OLE period, whichever is later, any new AESI (or new information related to a previously reported AESI) must be recorded in the AE eCRF and designated as an "AE of special interest."

For subjects participating in the OLE period, AESI will be assessed and recorded in the CRF of the AK002-027 double-blind treatment period database up until the start of the first OLE injection after the Day 85 visit and recorded in the CRF of the AK002-027 OLE period database beginning from the start of the first OLE injection after the Day 99 visit.

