15.1 Definition of Study Completion

A subject who completes visits through the Day 155 visit will be categorized as having completed the double-blind period of the study.

A subject who completes visits through the Day 85 visit and enters the OLE period of the study will be categorized as having completed the double-blind period of the study.

A subject who completes visits through the OLE Day 155 visit will be categorized as having completed the OLE period of the study.

The study is considered completed when the last subject completes the last study visit.

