20.9 Appendix 9: Open Label Extension Period (Optional)

20.9.1 Summary of the Open-Label Extended Dosing Period

Subjects who complete the double-blind, placebo-controlled treatment period (including the Day 85 study visit) and meet the open-label extended dosing eligibility criteria will be given the option to receive 6 doses of 300 mg lirentelimab SC through the open-label extension (OLE) dosing period.

On Day 85 (± 5 days) of the double-blind period, eligible subjects participating in the OLE period will begin following the OLE Schedule of Assessments (Table 10) and will no longer follow the Double-Blind Period Schedule of Assessments (Table 1). The subjects starting the OLE period on Day 85 of the double-blind period do not need to repeat any assessments that overlap with Day 85 from the double-blind period.

The OLE dosing period is summarized as follows:

- The Investigator will evaluate whether the subject is eligible for OLE. If eligible, the subject will be given the option to participate in the OLE period and receive 6 doses of open-label 300 mg lirentelimab SC administered every 2 weeks starting on Day 85 of the double-blind period, which will be considered Day 1 of the OLE period. OLE dosing may be delayed for up to 7 days after completion of the Day 85 visit.
- On Day 85, eligible subjects who choose to participate in the OLE period will begin following the OLE Schedule of Events (Table 10). Subjects starting the OLE period on Day 85 of the double-blind period do not need to repeat any assessments that overlap with Day 85 from the double-blind period.
- Day 1 of the OLE can occur up to 7 days following Day 85 of the double-blind period. In case Day 1 of the OLE is not the same as Day 85 of the double-blind period, applicable subjects (women of childbearing potential) will have to take a urine dipstick pregnancy test.
- Subsequent doses will be given on OLE Days 15, 29, 43, 57, and 71 (\pm 5 days).
- All differential blood counts will be blinded to the Sponsor and the site until after OLE Day 1 dosing.
- Subjects will remain at the site for at least 1 hour of observation after each dose. In the event of an IRR, the subject may require prolonged observation (>1 hour or until the symptoms resolve), as per Investigator discretion.

- Subjects will be followed for approximately 12 weeks after the last dose. Follow-up visits will occur on OLE Days 85, 127, and 155 (14, 56, and 84 [±5] days) after the last dose of open-label study drug.

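### Pregnancy capture closes nominally 84 days after the last dose, while the protocol requires contraception for at least 120 days, so pregnancies late in that period are outside the defined window and not solicited

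*Protocol*

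**What the plan says.** **Capture window.** Protocol 14.8.3 covers pregnancies in female subjects and in partners of male subjects, from first exposure "through the time of study completion or ET of the double-blind period or the OLE period, whichever is longer". It tells subjects to inform the Investigator of pregnancies that arise during the study.

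**Completion.** Protocol 15.1 defines this for each subject: "A subject who completes visits through the Day 155 visit will be categorized as having completed the double-blind period of the study", and "A subject who completes visits through the OLE Day 155 visit will be categorized as having completed the OLE period of the study". Someone who enters the OLE after Day 85 has also completed the double-blind period. The same section adds that the study as a whole is complete at the last subject's last visit.

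**Contraception.** Inclusion criterion 8 (Protocol 8.4) runs from screening to the end of the study or "for 120 days following the last dose of study drug, whichever is longer". Criterion 9 sets the same length for men with partners of childbearing potential, but limits its partner-pregnancy instruction to the time of study participation.

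**Unblinding.** Protocol 11.4 allows the blind to be broken "if there is a pregnancy during the pregnancy reporting period". The protocol does not define that period.

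**Testing.** Under Protocol 12.3.2, urine tests are done on dosing days, Day 8 and follow-up days. The last is therefore at the final follow-up visit.

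**The concern.** The protocol asks subjects to avoid pregnancy for longer than it undertakes to look for one. A pregnancy that begins late in the contraception period, or is recognised only then, comes after the last scheduled test, the last visit and the end of the capture window. The instructions to subjects in 14.8.3 and criterion 9 have lapsed by then as well.

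What is at stake is the completeness of safety data on pregnancies after exposure to an investigational antibody. The undefined period in 11.4 adds uncertainty about when a pregnancy is a ground for unblinding. That matters because follow-up through term under 14.8.3 is tied to having received lirentelimab.

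**Working it through.** **Inputs**
- Last double-blind dose (Protocol 10.4): "Day 57 (±5), Dose 5; and Day 71 (±5), Dose 6", so Day 71.
- Last double-blind visit (Protocol 13.13): "Day 155 (±5) or 84 Days Post-Dose – Follow-up Visit 3".
- OLE follow-up (Protocol 20.9.1): "Follow-up visits will occur on OLE Days 85, 127, and 155 (14, 56, and 84 [±5] days) after the last dose of open-label study drug". Table 10 places OLE Dose 6 at Week 22 and the last visit at Week 34.
- Contraception (criteria 8 and 9): at least 120 days after the last dose.
- ET visits (Protocol 13.13): 14, 56 or 84 (±5) days after the last dose, or sooner.

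**Step 1. Reproduce the protocol's own interval.**
- Double-blind: 155 − 71 = 84 days, as stated.
- OLE: (34 − 22) × 7 = 84 days. The OLE has the same interval, so entering it moves the gap to a later date without closing it.

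**Step 2. Gap for a subject who completes.** Gap = 120 − (days from last dose to end of capture).
- Nominal: 120 − 84 = 36 days.
- Last visit at 84 ± 5 days: 120 − 89 = 31 to 120 − 79 = 41 days.
- Day 71 and Day 155 windows both at their extremes: 120 − (160 − 66) = 26 to 120 − (150 − 76) = 46 days.

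**Step 3. Gap for a subject who leaves the study early.**

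| ET, days after last dose | Gap (days) |
|---|---|
| 56 | 120 − 56 = 64 |
| 14 | 120 − 14 = 106 |
| 0 (limiting case) | 120 |

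These rows apply to subjects who leave the study. Under Protocol 15.2, those who only stop study drug are encouraged to complete the 12-week follow-up; if they do, they have the gap in Step 2.

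**Step 4. Does another provision solicit these pregnancies?**
- The closing choice of the longer period in 14.8.3 is between the double-blind and OLE periods. It does not bring in the 120 days.
- Extended OLE follow-up (Protocol 20.9.1) collects only hematology, SAE and AESI.
- SAE recording (Protocol 14.2) also ends at Day 155 or 84 days after the last dose.
- No contact with subjects is scheduled after the last visit to ask about pregnancy.

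**The case against.** The strongest reply is that the two provisions do different jobs. One governs what subjects do and the other what the study collects, and a site can comply with both. That is correct: this is a misalignment of two windows rather than a strict contradiction.

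**Reporting and follow-up.** A reader might infer that these pregnancies would go unreported and unfollowed. The documents do not support that. Protocol 12.3.2 requires each pregnancy in a subject who received study drug to be reported within 24 hours of learning of it. Protocol 14.8.3 puts a similar duty on the Investigator, provides for follow-up through term in lirentelimab recipients, and makes congenital abnormalities reportable. None of these sentences has an end date, so a late pregnancy that becomes known can be reported and followed. What is missing is anything that makes it likely to become known.

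**Meaning of completion.** Protocol 15.1 also has a study-level definition, and 13.14 defines the end of each period by the last subject. On that reading, a subject who completes and whose last dose came at least 120 − 84 = 36 days before the last subject's has no gap. The wording of 14.8.3 pairs completion with ET, which happens to individuals, so the subject-level reading is likelier. On either reading the last subjects still have the gap.

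**Numbers affected.** A reader might count about 130 double-blind subjects plus the OLE entrants. That double-counts: OLE entrants are among the 130 and skip the double-blind Day 127 and Day 155 visits. Surgically sterile women and postmenopausal women with FSH above the stated limit are not of childbearing potential. About 65 subjects are randomized to placebo, and those who do not enter the OLE never receive lirentelimab.

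**Unblinding.** The consequence is limited. Treatment in the OLE is known, and the code for the others is released after database lock (Protocol 17.4).

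**Exposure window.** A reader might take the equation of 5 half-lives with 4 months in exclusion criterion 25 as the protocol's exposure window for pregnancy. It appears in a live-vaccine criterion, and no section defines such a window for pregnancy.

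**Conclusion.** The misalignment stands. For a subject who completes on schedule, capture ends a nominal 36 days before the 120-day point (31 to 41 days with the ±5-day window on the last visit). For a subject who leaves early the gap is longer, for example 64 days with ET at 56 days. Pregnancies in that interval are outside the defined window and unsolicited, although a site that learns of one still has duties to report it.

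This rests on reading completion at subject level and on counting from the last dose actually received. The population at risk is a subset of about 130 subjects, chiefly lirentelimab recipients; the documents do not give its size, so no expected number of pregnancies can be calculated. The primary and secondary efficacy results are untouched. The change is worth making as an inexpensive improvement to safety reporting.

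**What to change.** - Reconcile the end of the capture window and the subjects' duty to inform (14.8.3, and the partner-pregnancy instruction in criterion 9) with the contraception period in criteria 8 and 9. How long contraception should last is for the sponsor; the point is that the passages should agree.
- State in 14.8.3 whether completion means the subject's own last visit or the end of the study.
- Define the pregnancy reporting period in 11.4 by reference to the reconciled window.
- At the last or ET visit, instruct subjects to report their own or a partner's pregnancy until that period ends.

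The cost is minor edits to the protocol, consent form and site instructions, and acceptance of an occasional report after a subject has left the study. No visit or test is added.

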14.9 Medical Monitoring

Medical Monitoring is provided by the Sponsor for medically related questions.

14.10 Independent Data Monitoring Committee

An independent Data Monitoring Committee (iDMC) has been convened for this study. The iDMC will meet at established intervals (per the iDMC Charter) throughout the study and will also convene as necessitated by data and/or safety reviews.

At the sole discretion of the Sponsor, a separate independent statistical review committee may be convened and tasked to assess if there is evidence of a beneficial clinical effect prior to unblinding of the double-blind portion of the AK002-027 study. The primary and relevant secondary endpoints will be evaluated for this purpose. The statistical review committee will not be tasked with any determination as to stopping the study early for efficacy or futility. Greater detail concerning the statistical review committee will be provided in a separate charter.

14.11 Study Withdrawal Criteria

Participation of a subject will be discontinued in the event that:

- Occurrence of an exclusion criterion, which is clinically relevant and affects the subject's safety, if discontinuation is considered necessary by the Investigator and/or Sponsor.
- Rebounding of eosinophil counts to >1500/mL in subjects who entered the study with eosinophil levels >1500/mL and whose eosinophil counts were initially suppressed after study drug, as assessed by the Safety Monitor, may be withdrawn from the study at the instruction of the Medical Monitor.
- Serum transaminases (ALT and/or AST) >3 × ULN and total bilirubin >2 × ULN (confirmed by subsequent repeat) without an alternative explanation.
- Elevation of ALT or AST >3 × ULN (confirmed by repeat) with the appearance or worsening of symptoms felt by the Investigator to be potentially related to hepatic inflammation, such as fatigue, nausea, vomiting, right upper quadrant pain or tenderness, fever, and rash.

